5.4 Will you be using any survey software (such as Qualtrics)?

Yes (see question below)

No

If "Yes" which survey software will you be using? :

Harvard Qualtrics

INTERVIEWS/ORAL HISTORY/FOCUS GROUPS

Skip this section if not applicable.

5.5 Explain where interviews/focus groups will take place (including possible online venues such as Skype, online chat rooms, etc.)

Individual, semi-structured interviews will be conducted with a subset of consenting participants via Zoom for Harvard when follow-up surveys have been completed.

5.6 Describe any steps you will take to protect the participant's privacy during the interview/focus group.

Interviews will be conducted via Zoom for Harvard. Consenting students will be emailed a unique passcode and assigned participant ID to utilize as an identifier in the teleconference. Access to the meeting room will require entry of the passcode and will be manually managed by the research assistant via use of waiting rooms. Meetings will be audio-recorded and recordings will be stored on the encrypted Harvard Zoom cloud and as password-protected files on the PI's O365 Harvard OneDrive, such that research data will be accessible only to the research team while logged into Harvard's network via Cisco VPN. All recordings will be deleted after they have been transcribed and analyzed. Participants will be informed about the data collection, transfer, and storage process during the electronic consent procedure.

5.7 Describe the number of interviews/focus group sessions you anticipate for each participant and approximately how long you expect each interview/focus group to last.

At the time the email invitation for the fourth survey is sent to participants, it will also include an invitation to sign-up for optional interviews. The opportunity to participate in a paid individual interview will be offered to all participants in the study sample. Eligible students are those who (a) used the StriveWeekly platform at least once, (b) completed all study surveys, and (c) either identify as LGBTQ+ or want to provide feedback about program inclusivity for this community. Each student will participate in a single interview lasting approximately 30 to 60 minutes. It is anticipated that approximately 20 to 30 individual interviews will be conducted to achieve saturation.

5.8 Do you plan to quote the remarks of participants in your study?

Yes *(Refer to the consent template that you will be using for additional text to include.)*
 No

OBSERVATIONAL/ETHNOGRAPHIC RESEARCH

Skip this section if not applicable.

5.9 If you will be actively participating in the field (as in participant-observation), describe what this will entail.

5.10 Describe what and who will be observed and in what settings (such as public events, religious ceremonies, household activities, work meetings, internet chat-rooms and social media sites, etc.)

5.11 Will any observational data be considered private, according to the standards of that community?

Yes *(see below)*
 No

If "Yes" describe the information that would be private.

5.12 Will the data you collect contain any information that identifies specific individuals?

Yes
 No

5.13 Do you plan to quote the remarks of participants in your study?

Yes *(Refer to the consent template that you will be using for additional text to include.)*
 No

5.14 Will you notify participants that they are being observed?

Yes
 No *(see below)*

If "No" explain the circumstances why you would not be able to let participants know they are being observed.

5.15 If permission to observe participants is obtained, how will you ascertain whether there are individuals who do not want to participate, and how you will manage such a situation?

AUDIO-RECORDING/VIDEO-RECORDING/PHOTOGRAPHS

Skip this section if not applicable.

5.16 What type of recording will take place? (check all that apply)

- Audio-Recording
- Video-Recording
- Photography
- Other *(see below)*

If "Other" describe:

5.17 Explain what types of data will be recorded or photographed.

Individual interviews with a subset of students who have (a) used the StriveWeekly platform at least once, (b) completed all study surveys, and (c) either identify as LGBTQ+ or want to provide feedback about program inclusivity for the LGBTQ+ community will be conducted via Harvard Zoom. Each student will participate in a single interview lasting approximately 30 to 60 minutes. Interviews will be audio-recorded and only audio files will be sent out to the research team for transcription and subsequent coding for analysis.

5.18 If you will be collecting sensitive data, will you use any procedures to de-identify or anonymize the recordings or photographs?

Participants will be identified during the telemeeting in which the interview will take place using the same participant ID assigned to them for primary data analyses, per the Qualtrics ID key. Data will be automatically transcribed by Harvard Zoom software and reviewed for accuracy by [name]. Transcripts will additionally be thoroughly reviewed and any names or identifying information will be removed from the transcriptions immediately. All recordings will be deleted after they have been transcribed and analyzed.

5.19 Explain what will happen to the recordings/photographs at the end of the study.

Recordings will be stored in the encrypted Harvard Zoom cloud and as password-protected files on the PI's Harvard OneDrive. All recordings will be deleted after transcription is complete, files have been reviewed, and the analyses completed. While the transcribing process is underway, all transcripts will be saved on Harvard OneDrive. Transcripts will be retained for study record keeping purposes per institutional policy and future research use.

DECEPTION AND INCOMPLETE DISCLOSURE

Skip this section if not applicable.

Deception is the intentional misleading of a subject about the nature of the study. While withholding of full information is known as incomplete disclosure.

5.20 Describe what information will be withheld from participants or what misinformation will be provided to participants.

5.21 Explain why this research involves no more than minimal risk to participants and why it would be impracticable to carry out the research without the use of deception or incomplete disclosure.

5.22 Describe the plans for debriefing participants after their participation. If you do not plan to debrief participants, explain why.

Please be sure to attach a copy of the debriefing script (if applicable) to the "Local Sites Documents" section in the ESTR SmartForm.

DATA FROM OTHER SOURCES

Please complete this section if you are receiving data that is coming from other sources, for example, from a repository, medical record, institutional data, etc. This section does not pertain to data that is being collected through interaction or intervention as part of this study. Skip this section if not applicable.

5.23 When was the data collected?

- The data has already been collected to date (retrospective data).
- The data will be collected (prospective data)
- The data will include both types (retrospective and prospective)

5.24 Indicate the identifiability of the data when you collect and/or receive it:

- Will not contain any direct or indirect identifiers; will be anonymous.
- Will not be directly identifiable, but there will be a code held by the data source that links to the identities; will be coded.
- Will contain direct or indirect identifiers, but this research team will remove them upon receipt; will be de-identified data.

Will contain direct identifiers; will be identifiable.

5.25 Describe which data sets you plan to analyze, who is providing the data to you, and whether the data are public use data sets, restricted access datasets, or another type of dataset.

Data will be collected via the app (StriveWeekly) being tested in this intervention study. As the owner of StriveWeekly, [name] has been collaborating with developers from Harvard University Information Technology (HUIT) to duplicate the platform onto a Harvard-hosted instance. HUIT will provide [name] with access to the Harvard-hosted StriveWeekly app and its associated database. Students will have been informed about this data collection and transfer during the electronic consent procedure. Once all data collection is complete, [name] (StriveWeekly owner) will download the StriveWeekly user database onto a personal work laptop (due to remote work set-up) while logged into Harvard's network via Cisco VPN. Once it is downloaded as an Excel file, email addresses in the StriveWeekly user database will be linked and replaced by assigned participant IDs per the Qualtrics ID key, to which [name] in her role as the study PI has access. The platform database and Qualtrics surveys data will then all be merged into a password-protected master dataset using these participant IDs. This master file will thus have no identifying data within it. See 12.18 for details of StriveWeekly data storage. Also see corresponding DAT20-0492.

5.26 Provide an overview of the types of variables that are contained in the dataset.

The app's user database collects the following information, all based on user self-reported information:

Users Collection

1. User ID (randomly assigned by platform)
2. Name
3. Email (Harvard email addresses only)
4. Race / ethnicity
5. Gender
6. Year in college
7. Email timing preferences* (e.g., "On what days would you like to receive reminder emails?")
8. Personal program goals* (see examples:
<https://s3.amazonaws.com/documents.striveweekly.com/ExampleGoalPlans.pdf>)
9. Weekly check-ins* (e.g., "When you imagine your Life 2.0, did this week move you closer, further, or about the same?")

Logs / Histories Collections

10. User ID
11. Practice date
12. Virtual medals earned*
13. Practice activity logs* (drop-down list of skills for each week, e.g., "Practiced Yoga")
14. Self-reported stress and mood ratings 1-10*

The only variables that will be used for this research study are #7, 8, 9, 12, 13, & 14. The other variables will thus not be merged into the master dataset. Adherence and program completion will be defined *post hoc* based on spread of variables 13-14. Qualitative feedback from #9 may be reviewed for assessing individual program modules

5.27 Was the data you plan to analyze collected in a previous research study?

Yes (see below)

No

If "Yes" provide the title/name of the previous research study and which institution and researcher collected the data for the previous study. If the data were collected in a previous Harvard University research study, provide the ESTR number assigned to that study.

5.28 Will any of your data be obtained from internet sites (including data mining and data scraping activities)?

Yes (see question below)

No

If "Yes" what websites will you access to obtain the data?

Please know that it is your responsibility to check the terms of service of any websites from which you plan to collect data to determine whether your planned data collection is compatible with the terms of service.

striveweekly.fas.harvard.edu

5.29 Is the data publicly available on the internet (i.e., freely available without permission, sign-in, or other restrictions)?

Yes
 No

5.30 Do you plan to access any data that is Protected Health Information (PHI) under the HIPAA law (for example, data held by a hospital or other healthcare provider or insurer)?

Yes (see question below)
 No

If "Yes", which organization will provide the HIPAA PHI to you?

Per email from [name] (assigned DAT reviewer): "I ran your use case for StriveWeekly by my colleagues and we reached consensus that there's no direct FERPA coverage or any other regulatory aspect of concern where your registration or non-sensitive data collection within the platform goes."

How will permission to allow the use/disclosure of individual's protected health information (PHI) be obtained?

HRP-330 WORKSHEET: HIPAA, which may be found in the ESTR library, provides an overview of items pertaining to HIPAA that may be helpful to the study team.

5.31 Do you plan to access any data that is FERPA protected (data that are held as education records by an educational institution)?

Yes
 No

HRP-331 WORKSHEET: FERPA COMPLIANCE which may be found in the ESTR library provides an overview of items pertaining to FERPA that may be helpful to the study team.

5.32 Do you plan to obtain data that has been obtained under "Broad Consent" (as part of the 2018 Requirements)?

Yes
 No
 Uncertain

BIOLOGICAL MATERIALS FROM OTHER SOURCES

Please complete this section if you are receiving biological material from other sources, for example, from a biorepository, pathology department, commercial provider, etc. This section does not pertain to biological material that is being collected through interaction or intervention as part of this study. Skip this section if not applicable.

5.33 When was the biological material collected?

- The biological material has already been collected to date (retrospective).
- The biological material will be collected (prospective)
- The biological material will include both types (retrospective and prospective)

5.34 Indicate the identifiability of the biological materials when you collect and/or receive it:

- Will not contain any direct or indirect identifiers; will be anonymous.
- Will not be identifiable, but there will be a code held by the data source that links to the identities; will be coded.
- Will contain direct or indirect identifiers, but this research team will remove them upon receipt; will be de-identified data.
- Will contain direct identifiers; will be identifiable.

5.35 How will you obtain the material? (check all that apply)

- Residual clinical material
- Material obtained from a vendor
- Material that was collected as part of another research study (*please see below*)
- Other – (*see below*)

If you chose “another research study” provide the title/name of the previous research study and which institution and researcher collected the specimens for the previous study. If the specimens were collected in a previous Harvard University research study, provide the ESTR number assigned to that study.

If “another research study” or “Other” please specify:

5.36 Will the material consist of any of the following? (check all that apply)

- Embryonic tissue
- Embryonic stem cells
- Stem cells
- Fresh human fetal tissue
- None of the above

5.37 Provide an overview of the types of variables that will accompany the biological materials (for example, identifiable data such as names, date of birth, addresses, or any data that are considered sensitive).

DEVICES

Skip this section if not applicable.

5.38 List the device(s) that you plan to use in this study (add additional lines as necessary):

Device Brand Name	Generic/Common Name	Manufacturer	Purpose	Function/Operation

5.39 Is the device(s) that you plan to use FDA-approved/cleared?

Yes
 No

5.40 If any of the devices that you plan to use require a certified professional to operate, please explain who is certified to operate this device and whether they are on your study team.

Please complete HRP-307 WORKSHEET: DEVICES which may be found in the ESTR library and attach to the “Local Site Documents” section in the ESTR SmartForm.

DRUGS

Skip this section if not applicable.

5.41 List the drug(s) or biologic(s) that you plan to use in this study (add additional lines as necessary):

Drug/Biologic Brand Name	Generic/Common Name	Manufacturer	Purpose	Function/Operation

5.42 Is the drug(s)/biologic(s) that you plan to use FDA-approved/cleared?

Yes
 No

5.43 Please explain who is qualified to dispense this drug/biologic and whether they are on your study team.

Please complete HRP-306 WORKSHEET: DRUGS which may be found in the ESTR library and attach to the “Local Site Documents” section in the ESTR SmartForm.

6. RISK AND BENEFIT ASSESSMENT

6.1 Describe the foreseeable risks associated with your study. Please include discussion of any physical risks and non-physical risks, such as economic, psychological, social, and legal harms.

Loss of confidentiality is always a risk in studies using human subjects.

Participants may experience **mild discomforts** such as:

- mild boredom or fatigue when completing surveys
- mild annoyance for receiving survey reminder emails
- mild discomfort upon self-reflection about emotional functioning as prompted by surveys

Although we will not be prompting for sensitive data in our surveys, students may of their own volition self-report **potentially sensitive risk data** within open-ended response fields in posttest and follow-up surveys. We do not anticipate such cases being common though, given that the two open-ended questions that we are posing is unlikely to prompt sensitive date. For reference the two questions are: (1) “Overall, what was the most helpful part of this program? What did you like best? What most encouraged you to complete the program?” and (2) “And what was/were the biggest barrier(s) to completing the program? What would need to change to make this program better?”

We do not anticipate any serious risks. Supporting this claim, in a prior open trial and a prior randomized controlled trial there were no students reporting adverse events due to the intervention (as documented by open-ended responses in posttest feedback surveys).

6.2 Describe the steps that you will take to minimize risks to your participants (for example, using pseudonyms or a coding system, etc.)

Loss of confidentiality will be minimized by the following procedures:

1. All consent/assent forms and surveys will be electronic via the Harvard Qualtrics, which is encrypted and will only be accessible by the PI.
2. The Harvard Qualtrics surveys will be configured to use an auto-generated participant ID, kept separate from the ID key (which is associated with their Harvard Key email address)
3. All datasets downloaded on the PI's laptop for analyses (over a secure wifi connection) will have all identifying data (e.g., names, emails) removed.
4. See DAT20-0492 uploaded documentation for platform security info.
5. The master dataset will be password-protected and stored on the PI's Harvard OneDrive.
6. Any qualitative findings will be presented in an aggregated and de-identified way. Selected quotes will be accordingly redacted as necessary.

Mild discomforts due to survey fatigue will be reduced by optimizing Qualtrics surveys to be easy to answer and minimizing the number of reminder emails sent. Mild discomforts due to self-reflection about psychological symptoms and stressful experiences will be mitigated by provided resource referral info (more info in next item).

Regarding potential sensitive risk data: We will not be asking any questions that prompt students to report on intent to harm themselves or others. Our consent form will warn students (see the “Clinically-Relevant Results” section of consent form) that their individual responses on their StriveWeekly user accounts or in open-ended survey responses will not be monitored during the study, and thus they should not use such text fields to communicate to the research team or Harvard admin about any health concerns. We will also remind students within the posttest and follow-up survey instructions that they are discouraged from entering sensitive data. Nevertheless, we will provide students with referral information to mental health services (e.g., crisis hotlines, counseling center services) in (A) the auto-email sent after a respondent completes a survey, and (b) under the “campus” section of StriveWeekly’s platform.

6.3 Are provisions needed for medical and/or psychological support resources (for example, in the event of research-related distress or incidental findings)?

Yes

No

6.4 If applicable, what steps will you take if a participant becomes distressed during your study or reports intent to harm themselves or others?

We will not be asking any questions that prompt students to report on intent to harm themselves or others. Our consent form will warn students (see the “Clinically-Relevant Results” section) that their

individual responses on their StriveWeekly user accounts or in open-ended survey responses will not be monitored during the study, and thus they should not use such text fields to communicate to the research team or Harvard admin about any health concerns. Nevertheless, we will provide students with referral information to mental health services (e.g., crisis hotlines, counseling center services) in (A) the auto-email sent after a respondent completes a survey, and (b) under the “campus” section of StriveWeekly’s platform.

6.5 Describe any potential direct benefits to participants in the study. If there are no individual benefits, indicate as such.

Students may benefit psychologically from the StriveWeekly program, as supported by the demonstrated small effect sizes of anxiety and depression symptom improvement in the prior RCT testing StriveWeekly. Given that two of the skill weeks encourage physical exercise, sleep hygiene, and social skills, students may experience physical health and social life benefits if the intervention helps them to engage in more of such activities.

6.6 Describe any potential benefits to society.

The results of the research may advance our knowledge about disseminating effective lifestyle programming on university campuses. With the rise of personalized medicine, understanding individual differences in prevention program response will help us better tailor programs to engage and help more individuals. With many universities feeling uncertain about how they can support their students emotionally during remote learning and the COVID-19 pandemic, this trial may demonstrate if such online mental health skills programs are a worthwhile service.

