The below sections contain additional questions depending on the type of research that you are conducting and is meant to supplement the study overview. Please complete each section, as applicable.

SURVEYS/ QUESTIONNAIRES/PSYCHOMETRIC TESTING

Skip this section if not applicable.

5.2 List the names of all surveys/questionnaires/psychometric tests to be used in this study and a description of any that are not standard/formally named (such as study-specific questionnaires).

See full details in uploaded measure battery.

1. **Self-report demographic questionnaire** (age, gender, ethnicity, academic year).
2. **Branding feedback.** There will be a few questions about if students would have been more or less likely to sign-up for the program had it been under a different name (e.g. "The Happiness Challenge")
3. **Treatment Motivation Questionnaire (TMQ).** Questions from the Treatment Motivation Questionnaire (Ryan, Plant, & O'Malley, 1995) have been minimally adapted to apply to an online mental health promotion program instead of a treatment. Questions from the help-

seeking subscale were removed. This 20-question measure will assess participants' reasons for signing up and expectations for completing the program. The TMQ has significant predicted intervention completion in other research studies, for example in-person alcohol treatment (Ryan et al., 1995) and online trauma treatment (Alfonsson et al., 2016).

4. **Depression Anxiety and Stress Scale.** The primary symptom outcome measure will be the 21-item version of the Depression Anxiety and Stress Scale (DASS-21), which assesses self-reported symptoms related to depression, anxiety, and stress. The DASS-21 has demonstrated high internal consistency (.83 - .90) and good construct validity in university student samples (Norton, 2007). Note: There are no questions related to suicidality.
5. **Perceived Stress Scale.** This measure is a 10-item scale that is the most widely used psychological instrument for measuring the perception of stress. It is a measure of the degree to which situations in one's life are appraised as stressful. Items were designed to tap how unpredictable, uncontrollable, and overloaded respondents find their lives.

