6. **Self-reported service use.** Students will be asked to indicate past and current use of health-related services on- and off-campus using a checklist of common resources/services (e.g., off-campus therapy, psychiatry at HUHS, etc.) as well as a write-in "other" option.
7. **Technology use.** Students will be asked to indicate the types of devices they use, their internet access, health data settings, etc.
8. **Checklists / weekly hour estimates of extracurriculars and regular behaviors.** See uploaded battery.
9. **Life Events Checklist.** Items combined from the following standardized measures: Life Events Scale for Children, Adolescent Perceived Events Scale, and Life Events Checklist for DSM-5 (LEC-5). Some original items added, including COVID-19-related items.
10. **General Belongingness Scale.** A standardized 12-item measure to assess a sense of general belongingness, which has been previously validated in student samples.

Pilot / Posttest / Follow-Up Survey Only

11. **Program satisfaction.** The posttest and follow-up surveys will include questions about experiences with the program for the respective group that just completed the intervention. This 5-item measure is adapted from the Client Satisfaction Questionnaire (Larsen, Attkisson, Hargreaves, & Nguyen, 1979), which has been found to be an appropriate measure of satisfaction with high internal consistency and concurrent validity across a broad range of intervention contexts (e.g., children's outpatient mental health services, Copeland, Koeske, & Greeno, 2004; adult outpatient setting, De Wilde & Hendriks, 2005; adult residential treatment setting, Kelly et al., 2018).
12. **Module preferences.** Students will be asked to rank the modules in order of the most to least favorite.
13. **Open-ended feedback.** There will be an open text field for participants to write any feedback they had about their experience.
14. **Tech-based intervention barrier scale.** A 10-item self-report scale to assess barriers experienced by users of tech-based interventions (Ramos, Hammons, Chavira, & Rith-Najarian, 2019)

Follow-Up Interview

15. **Study-specific semi-structured interview.** A subsample of students will be asked a series of open-ended questions to gather feedback about their experience with StriveWeekly and invite proposed adaptions to improve acceptability, feasibility, and engagement for a targeted sample of students endorsing identification with the LGBTQ+ community.

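### No structured adverse-event or individual-worsening assessment is described, although the DASS-21 in both arms could supply one; silence in the open-text fields would say little about harm

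*Protocol*

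**What the plan says.** Protocol section 6.1 anticipates no serious risks. Its evidence is that, in one earlier open trial and one earlier randomized trial, there were "no students reporting adverse events due to the intervention (as documented by open-ended responses in posttest feedback surveys".

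For the present trial, 6.1 opens its account of sensitive content with "Although we will not be prompting for sensitive data in our surveys" and gives the two open-ended prompts. The first begins "Overall, what was the most helpful part of this program? What did you like best"; the second asks "And what was/were the biggest barrier(s) to completing the program? What would need to change to make this program better". Section 6.2 adds: "We will also remind students within the posttest and follow-up survey instructions that they are discouraged from entering sensitive data". Sections 6.2 and 6.4 also say that open-text responses are not monitored during the study and that the consent form warns students against using those fields to raise health concerns.

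Section 5.2 item 11 directs the program-experience questions to students "for the respective group that just completed the intervention". Item 13 is a general feedback field. Item 4 names the DASS-21 as the primary symptom measure and states that "The DASS-21 has demonstrated high internal consistency (.83 - .90) and good construct validity in university student samples". Section 5.1 opens the posttest to both the intervention and the waitlist group.

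The SAP's Data analysis paragraph plans piecewise mixed models of change in outcome scores with random participant intercepts and slopes, effect sizes from estimated marginal means, and moderators and mediators chosen post hoc. It mentions no adverse events and no individual deterioration.

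**The concern.** The protocol's low-risk argument depends on nobody having volunteered a harm in free text. This trial also collects free text, under prompts that do not ask about getting worse and with instructions that steer students away from saying so. At posttest, the program-experience items go only to the intervention group, so they have no waitlist comparison.

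A small average benefit, such as the d = 0.25 that section 4.2 reports for the earlier randomized trial, is compatible with some students deteriorating. Section 4.1 includes the prevention of worsening in the aim, so individual worsening falls within the trial's own question. For a self-guided program offered to a whole campus, it would be a loss to finish a randomized trial with the relevant data in both arms and no planned estimate of how many students got worse.

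**Working it through.** The plan states no harm rate, sample size or deterioration threshold, so there is no figure of its own to reproduce. There are three checks.

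**1. What an absence of open-text reports can show.** Let n be the number of open-text respondents, p the true proportion harmed, and s the chance that a harmed respondent writes it down. The documents give none of these, so all values are assumptions.

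- Probability of no report: (1 − p·s)^n. With p = 0.05 and s = 0.05 this is 0.9975^n: 0.61 at n = 200, 0.37 at n = 400 and 0.14 at n = 800.
- Upper 95% bound on p after zero reports: (1 − 0.05^(1/n)) / s. At n = 200 the numerator is 1.49%. The bound is 1.5% if s = 1, 5.9% if s = 0.25, 14.9% if s = 0.10 and 29.7% if s = 0.05.
- At n = 800 the bounds for the same values of s are 0.37%, 1.5%, 3.7% and 7.5%.

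The result depends on s, and the instructions in 6.2 push s down. As s approaches 0, no reports are expected whatever p is.

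**2. A worsening threshold from the DASS-21.** Reliable change is 1.96 × SD × √(2(1 − r)), with SD the baseline standard deviation and r the reliability.

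- r = .90: 1.96 × √0.20 = 0.877 SD.
- r = .83: 1.96 × √0.34 = 1.143 SD.

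The range .83 to .90 comes from section 5.2 item 4. It is internal consistency, and the item does not say which DASS-21 score it describes. Internal consistency does not capture ordinary fluctuation over the weeks between surveys, so some waitlist students will cross the line too. The informative quantity is therefore the difference between arms.

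**3. Precision of a by-arm comparison.** Assume 300 students per arm with posttest data and 10% worsening in each.

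- Ignoring clustering: 1.96 × √(2 × 0.10 × 0.90 / 300) = 0.048, or ±4.8 percentage points.
- Section 5.1 lists 7 houses and 2 freshman yards in the immediate arm, and 6 houses and 3 yards in the delayed arm. That is 9 units per arm and 18 in all, or 300 / 9 = 33.3 students per unit on the assumed size.
- Design effect: 1 + (33.3 − 1) × ICC. ICC 0.01 gives 1.323, 0.02 gives 1.647 and 0.05 gives 2.617.
- Half-widths: 4.8 × √1.323 = 5.5, 4.8 × √1.647 = 6.2 and 4.8 × √2.617 = 7.8 points.

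Unequal unit sizes and a t reference distribution for 18 units would widen these somewhat.

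**The case against.** Much can fairly be said for the plan.

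- The sentence in 6.1 describes earlier trials. A reader might infer that open text is this trial's adverse-event channel and that the trial will report none. The documents say neither, nor do they say that the earlier surveys used these prompts or the discouraging instruction.
- A reader might also infer that free text is the only place where harm could appear. That is not so. The DASS-21 and the Perceived Stress Scale (5.2 items 4 and 5) are in the survey battery. For program users, the app records mood and stress ratings and a weekly check-in that allows an unfavourable answer (5.26). A student who worsened and answered the posttest is recorded as having a higher score.
- It would be too strong to say that zero open-text reports would be false or an artefact. The second prompt and the general feedback field could draw out a bad experience.
- The SAP is more than a comparison of means: it has random participant slopes and moderator analyses.
- The measure battery and the full consent form are not in the supplied text, so absence can be stated only for what is supplied.

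These points limit the claim but leave the gap. None of the measures that could show worsening is designated for harm. Random slopes and moderators chosen after the data are seen do not yield a worsening rate by arm. An absence of free-text reports remains uninformative. The proposed measure is also imprecise at the assumed size, but an interval of known width tells the reader more than silence does.

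**Conclusion.** The point stands as a cheap improvement; it is not a flaw in the primary comparison. In the supplied text, no structured adverse-event or deterioration assessment is described, the low-risk statement rests on unprompted free text from earlier trials, and the SAP plans no by-arm worsening rate from a measure that both arms complete.

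The documents do not show that harm occurred, that harm was missed in the earlier trials, or that this trial will claim there was none. They support only the conclusion that silence in these fields could not be read as evidence of safety.

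On size, the reliable-worsening threshold is about 0.88 to 1.14 baseline SD if the quoted reliabilities apply to the score used. The arm difference would be known to about ±5.5 to 7.8 percentage points, on the assumptions of 300 per arm, 10% worsening and ICC 0.01 to 0.05. The reporting probabilities in the first check are illustrations, not estimates.

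**What to change.** Add to the SAP, as a harm outcome, the proportion in each arm whose DASS-21 total rises from baseline to posttest by more than 1.96 × baseline SD × √(2(1 − r)), stating the reliability used for that score and its source. Report both proportions and their difference with an interval that accounts for the 18 randomized residential units. Add a sensitivity analysis for posttest nonresponse, since students who worsened may be less likely to answer. Do not cite an absence of open-text reports as evidence of no adverse events.

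A closed item in both arms asking whether symptoms got worse is optional. Students know their assignment, the item overlaps with change on the DASS-21 and Perceived Stress Scale, and it is possible only while surveys are open.

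The SAP text comes from an August 2020 proposal and its cover date (June 2023) falls after the protocol's timeline ends. The tabulation needs no new data, but if outcomes have already been examined it should be labelled as added afterwards.

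The cost is one extra analysis, and a harm figure that may look less favourable than none reported.
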